6.1 Study Intervention(s) Administered

The study interventions to be used in this study are outlined in Table 2.

Country-specific requirements are noted in Appendix 7.

1 able 2 Study Intervention	Table 2	Study Interventions
-----------------------------	---------	---------------------

Arm	Arm Type	Intervention	Intervention	Dose	Unit Dose	Dosage	Route of	Regimen/	Use	IMP or	Sourcing
Name		Name	Туре	Formulation	Strength(s)	Levels	Administration	Treatment		NIMP/	
								Period		AxMP	
Belzutifan	Experimental	Belzutifan	Drug	Tablet	40 mg tablet	120 mg	Oral	QD	Test Product	IMP	Central
Everolimus	Active Comparator	Everolimus	Drug	Tablet	10 mg tablet	10 mg	Oral	QD	Comparator	IMP	Central; local supply as needed

Abbreviations: EEA=European Economic Area; IMP=investigational medicinal product; NIMP/AxMP=noninvestigational/auxiliary medicinal product; QD=once daily. Belzutifan: 120 mg dose should be made up of 3×40 mg tablets.

Everolimus: 2.5 mg and 5 mg tablets are provided for dose reductions as outlined in Section 6.6.2.

Note: The classification of IMP and NIMP/AxMP in this table is based on guidance issued by the European Commission and applies to countries in the EEA. Country differences with respect to the definition/classification of IMP and NIMP/AxMP may exist. In these circumstances, local legislation is followed.

All supplies indicated in Table 2 will be provided per the "Sourcing" column depending upon local country operational requirements. If local sourcing, every attempt should be made to source these supplies from a single lot/batch number where possible (eg, not applicable in the case where multiple lots or batches may be required due to the length of the study, etc.).

Refer to Section 8.1.8 for details regarding administration of the study intervention.

6.2 Preparation/Handling/Storage/Accountability

6.2.1 Dose Preparation

6.2.1.1 Belzutifan

Belzutifan tablets are supplied by the Sponsor as an immediate-release tablet in 1 dose strength, 40 mg, for oral administration.

The 40-mg strength tablets will be supplied in HDPE bottles with induction-seal liners and a child-resistant closure. Each bottle of study intervention will contain 90 tablets of a single strength of belzutifan (40 mg) and a desiccant insert.

The Pharmacy Manual contains additional information.

6.2.1.2 Everolimus

Everolimus will be available as 10-mg, 5-mg, and 2.5-mg tablets. Refer to the package insert for additional information. Everolimus is to be administered as the tablet formulation only; the suspension formulation is not to be used.

All dosages of everolimus (10-mg, 5-mg, and 2.5-mg) will be available in commercial packaging if locally sourced.

6.2.2 Handling, Storage, and Accountability

The investigator or designee must confirm appropriate temperature conditions have been maintained during transit for all study intervention received, and any discrepancies are reported and resolved before use of the study intervention.

Only participants enrolled in the study may receive study intervention, and only authorized site staff may supply or administer study intervention. All study interventions must be stored in a secure, environmentally controlled, and monitored (manual or automated) area in accordance with the labeled storage conditions with access limited to the investigator and authorized site staff.

The investigator, institution, or the head of the medical institution (where applicable) is responsible for study intervention accountability, reconciliation, and record maintenance (ie, receipt, reconciliation, and final disposition records).

60

For all study sites, the local country Sponsor personnel or designee will provide appropriate documentation that must be completed for drug accountability and return, or local discard and destruction if appropriate. Where local discard and destruction is appropriate, the investigator is responsible for ensuring that a local discard/destruction procedure is documented.

The study site is responsible for recording the lot number, manufacturer, and expiry date for any locally purchased product (if applicable) as per local guidelines unless otherwise instructed by the Sponsor.

The investigator shall take responsibility for and shall take all steps to maintain appropriate records and ensure appropriate supply, storage, handling, distribution, and usage of study interventions in accordance with the protocol and any applicable laws and regulations.

6.3 Measures to Minimize Bias: Randomization and Blinding

6.3.1 Intervention Assignment

Treatment allocation will occur centrally using an IRT system. There are 2 study intervention treatment groups. Participants will be assigned randomly in a 1:1 ratio to belzutifan study intervention or everolimus study intervention.

6.3.2 Stratification

Randomization will be stratified by the following factors:

- IMDC prognostic scores [Cella, D. 2011] [Heng, D. Y., et al 2013]: 0 vs 1-2 vs 3-6
- Number of prior VEGF/VEGF receptor targeted therapies for advanced RCC: 1 vs 2-3

The IMDC prognostic factors are the following:

- Clinical Risk Factors
 - Low KPS score (<80%)
 - Time from diagnosis to initiation of first-line treatment <1 year
- Laboratory Risk Factors
 - Low hemoglobin (<LLN)
 - High corrected serum calcium (>ULN)
 - High neutrophils (>ULN)
 - High levels of platelets (>ULN)

Prognosis is based on the number of IMDC factors present and determined as follows:

- Favorable prognosis: 0 risk factors
- Intermediate prognosis: 1-2 risk factors
- Poor prognosis: ≥ 3 risk factors

The most recent evaluations used to establish eligibility should be used to determine the IMDC category for stratification, and only results from central laboratory testing will be considered for the laboratory factors.

6.3.3 Blinding

This is an open-label study; therefore, the Sponsor, investigator, and participant will know the intervention administered.

6.4 Study Intervention Compliance

Interruptions from the protocol-specified treatment for >28 days require consultation between the investigator and the Sponsor and written documentation of the collaborative decision on participant management.

The investigator or his/her designated and qualified representatives will dispense study intervention (except locally sourced everolimus) only to participants enrolled in the study in accordance with the protocol. The study intervention must not be used for reasons other than that described in the protocol.

Participants should be given clear instructions on how and when to take their study intervention. Participants will self-administer belzutifan, except at Weeks 1, 3, and 5 when belzutifan dosing will occur during the clinic visit.

All participants must bring back to the clinic their bottle(s)/packages of belzutifan/everolimus at the appropriate scheduled visit. Participants will be instructed to notify study-site personnel of missed doses.

Study-site staff will make tablet counts at clinic when tablets are returned, the remaining tablets will not be returned to the participant, but will be retained by the investigative site (if permitted) until reconciliation is completed by the study monitor, if possible.

Compliance should be based on participant reporting and confirmed by tablet count where possible. Issues with compliance should be discussed with the participant and addressed as deemed appropriate by the investigator.

Participants who fail to comply with the dosing requirements of the study may be withdrawn from the study.

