7 DISCONTINUATION OF STUDY INTERVENTION AND PARTICIPANT WITHDRAWAL

7.1 Discontinuation of Study Intervention

Discontinuation of study intervention does not represent withdrawal from the study.

As certain data on clinical events beyond study intervention discontinuation may be important to the study, they must be collected through the participant's last scheduled followup, even if the participant has discontinued study intervention. Therefore, all participants who discontinue study intervention prior to completion of the protocol-specified treatment period will still continue to participate in the study as specified in Section 1.3 and Section 8.11.3.

Participants may discontinue study intervention at any time for any reason or be discontinued from the study intervention at the discretion of the investigator should any untoward effect occur. In addition, a participant may be discontinued from study intervention by the investigator or the Sponsor if study intervention is inappropriate, the study plan is violated, or for administrative and/or other safety reasons. Specific details regarding procedures to be performed at study intervention discontinuation are provided in Section 8.1.9 and Section 8.11.3.

A participant must be discontinued from study intervention, but continue to be monitored in the study for any of the following reasons:

- The participant or participant's legally acceptable representative requests to discontinue study intervention.
- Radiographic disease progression outlined in Section 8.2.1 (exception if the Sponsor approves treatment continuation following BICR-verified disease progression per RECIST [Section 4.1]).
- Any progression or recurrence of any malignancy, or any occurrence of another malignancy that requires treatment.
- Unacceptable AEs or toxicities (Section 6.6).
- The participant interrupts study intervention administration for >28 consecutive days without Sponsor consultation.
- The participant has a medical condition or personal circumstance which, in the opinion of the investigator and/or Sponsor, placed the participant at unnecessary risk from continued administration of study intervention.
- The participant has a confirmed positive serum or highly sensitive urine pregnancy test.
- Sponsor discontinuation of study.

As described in Section 4.1, treatment may continue beyond BICR-verified disease progression, but requires Sponsor consultation and approval. If approved by the Sponsor,

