7.2 Participant Withdrawal From the Study

A participant must be withdrawn from the study if the participant or participant's legally acceptable representative withdraws consent from the study.

If a participant withdraws from the study, they will no longer receive study intervention or be followed at scheduled protocol visits.

Specific details regarding procedures to be performed at the time of withdrawal from the study, as well as specific details regarding withdrawal from FBR, are outlined in Section 8.1.9. The procedures to be performed should a participant repeatedly fail to return for scheduled visits and/or if the study site is unable to contact the participant are outlined in Section 7.3.

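### Section 6.4 lets a site withdraw a participant from the study for poor dosing compliance, against Section 7.1 and the OS and imaging follow-up rules

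*Protocol*

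**What the plan says.** **Protocol 6.4 (Study Intervention Compliance):** "Participants who fail to comply with the dosing requirements of the study may be withdrawn from the study". What the participant leaves is the study, not the study drug. The rule is permissive.

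**Protocol 7.1 (Discontinuation of Study Intervention):**
- It sets the general principle: "Discontinuation of study intervention does not represent withdrawal from the study". Those who stop treatment early remain in the study.
- Its discretionary rule is that "a participant may be discontinued from study intervention by the investigator or the Sponsor if study intervention is inappropriate, the study plan is violated".
- Its mandatory list opens "A participant must be discontinued from study intervention, but continue to be monitored in the study for any of the following reasons", and one entry is "The participant interrupts study intervention administration for >28 consecutive days without Sponsor consultation".

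**Protocol 7.2 (Participant Withdrawal From the Study):** one mandatory ground is named: "A participant must be withdrawn from the study if the participant or participant's legally acceptable representative withdraws consent from the study". The consequence follows: "If a participant withdraws from the study, they will no longer receive study intervention or be followed at scheduled protocol visits". Non-compliance is not mentioned.

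**Follow-up rules:** the synopsis and 8.11.3.3 continue survival follow-up until death, withdrawal of consent or the end of the study. Section 4.1 adds loss to follow-up and early termination. The imaging stop lists in 8.2.1.2, 8.2.1.3 and 8.11.3.2 name BICR-verified progression, new anticancer treatment, pregnancy, death, consent withdrawal and study end. None of these lists includes non-compliance.

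**Analysis:** both primary endpoints use the ITT population (Protocol 9.5.1). OS without a documented death is censored when last known alive (Protocol 9.6.1.2). PFS without an event or new therapy is censored at the last disease assessment (SAP 3.6.1.1).

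**The concern.** The protocol otherwise separates leaving treatment from leaving the study. Section 6.5.1 shows the intent: a participant who needs a prohibited therapy comes off treatment but stays in the study for disease status and survival. Section 6.4 departs from this. It creates an exit from the study at the site's discretion, after randomization, by staff who know the assigned arm.

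ITT analysis needs outcomes on everyone randomized, whatever they took. People who stop taking tablets in a late-line cancer trial may be sicker or less tolerant of their drug than those who continue. If they are removed and censored, the assumption of non-informative censoring behind the log-rank test and Cox model becomes doubtful. OS has the least slack, because the SAP assumes almost no OS dropout.

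**Working it through.** **1. The texts side by side**

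| Situation | Where | Consequence |
|---|---|---|
| Fails to comply with dosing | 6.4 | May be withdrawn from the study |
| Study plan violated | 7.1, discretionary | May be taken off study intervention; remains in the study |
| Interruption >28 days without Sponsor consultation | 7.1, mandatory list | Must come off study intervention; monitoring continues |
| Needs a prohibited therapy | 6.5.1 | Off treatment; stays in the study |
| Withdraws consent | 7.2 | Must be withdrawn; no scheduled visits |

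A participant who repeatedly misses doses can fall under the first two or three rows at once, with different consequences for follow-up.

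**2. The plan's own OS figures reproduce**

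Inputs (SAP 3.9, Table 11): 736 participants at 1:1, control median 20.0 months, HR 0.75, 22-month accrual, analysis at month 49, about 1% annual dropout, 483 deaths, one-sided alpha 0.019.

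- Fixed-design power = Φ(√(483/4) × |ln 0.75| − 2.075) = Φ(3.161 − 2.075) = 86.1%. With the Table 11 bounds at 300, 410 and 483 deaths it is 85.3%, against 85.4% stated.
- Monthly hazards are ln 2/20 = 0.03466 (everolimus) and 0.75 times that, 0.02599 (belzutifan). The dropout hazard is −ln(0.99)/12 = 0.000838. Expected deaths at month 49 are 264 + 226 = 490, against about 483 stated.
- Expected OS dropouts are deaths × dropout hazard / death hazard: 264 × 0.000838/0.03466 = 6.4, plus 226 × 0.000838/0.02599 = 7.3, or about 14 in all.

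**3. Loss of information, if withdrawal is unrelated to prognosis**

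Raising annual OS dropout in both arms from 1% to 2%, 3%, 5% or 10% lowers expected deaths at month 49 from 490 to 483, 477, 465 or 435. Group-sequential power goes from 85.8% to 85.3%, 84.8%, 83.9% or 81.3%. Because the analyses are event-driven, part of this would appear as delay.

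**4. Bias, if withdrawal is related to prognosis (all rates assumed)**

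I simulated the SAP design, with non-compliers withdrawn at 1 to 6 months and censored there. The cohort was large (4 million, deaths scaled to 736), so Monte Carlo error in each HR is about 0.001.

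| Non-compliers, everolimus / belzutifan | Their death hazard | OS HR, all followed | OS HR, withdrawn and censored | Shift | Deaths lost |
|---|---|---|---|---|---|
| 3% / 1% | doubled | 0.741 | 0.748 | +0.007 | 10 |
| 5% / 2% | doubled | 0.738 | 0.748 | +0.010 | 18 |
| 8% / 2% | doubled | 0.725 | 0.744 | +0.020 | 26 |
| 2% / 5% | doubled | 0.766 | 0.753 | −0.013 | 18 |
| 5% / 5% | unchanged | 0.751 | 0.751 | 0.000 | 21 |

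For scale, 5% and 2% of 368 per arm are 18 + 7, about 26 people before rounding, against the 14 OS dropouts planned. The full-follow-up HR differs from 0.75 in rows 1 to 4 because the extra hazard is itself placed unequally between arms. The shift column is the effect of the withdrawal rule. A positive shift works against belzutifan and a negative one favours it.

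**The case against.** The strongest reply is that the protocol already protects follow-up.

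- **Specific rules govern.** The synopsis, 8.11.3.3 and the imaging stop lists leave no room for ending follow-up over compliance. That is so, but it shows what 6.4 conflicts with. It does not tell a site which text to follow.
- **Section 7.2 may not reach site-initiated removal.** Its sentence is conditional on the participant withdrawing, and it ends scheduled visits only. Survival status can be obtained by telephone or record review, and 8.11.3.3 lets the Sponsor request survival contacts before an analysis. This stands: loss of survival data is possible, not certain. Scheduled imaging is more exposed.
- **A reader might infer that 7.2 makes consent withdrawal the sole ground for leaving the study, so that 6.4 breaks it directly.** The text does not say so. It says when withdrawal must happen, and a permissive rule elsewhere does not contradict that. The conflict is with 7.1 and the follow-up rules.
- **A reader might infer that 6.4 and 7.1 name the same trigger.** They overlap, but the wording differs.
- **PFS has some cover.** The SAP assumes 20% annual PFS dropout, and sensitivity analysis 2 counts treatment discontinuation as progression in most cases without a documented event. This is partial cover for PFS. The available text states no matching OS analysis.
- **It may be too late.** The protocol is dated November 2024 and the SAP was updated for IA1 in November 2022, so the final analysis may have passed. The documents do not give the actual analysis dates, so this remains an inference.

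**Conclusion.** The inconsistency is real and can be checked from the text alone. Section 6.4 permits an exit from the study that 7.1 and the follow-up rules do not recognise. Used literally, it could censor both primary endpoints in participants who have not withdrawn consent.

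The effect on results is unknown. A reader might infer that the censoring is arm-dependent or has biased the OS comparison. The documents do not support that: they give no non-compliance rate, no split by arm and no link to prognosis. Open-label treatment and different safety profiles make a difference plausible, no more. The shifts of about 0.01 to 0.02 in the OS hazard ratio rest wholly on assumed rates and a doubled hazard, change sign with the arm affected, and vanish when prognosis is unchanged. Every modelled HR stays below the 0.822 bound at the final OS analysis. Severity is minor to moderate.

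**What to change.** In 6.4, replace withdrawal from the study with discontinuation of study intervention, cross-referring to 7.1. Add that non-compliance alone does not end BICR imaging follow-up (8.2.1.3, 8.11.3.2) or survival follow-up (8.11.3.3). Whether and when to stop study intervention for non-compliance is left as it is.

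The cost is one or two sentences in an amendment and a note to sites. There are no new procedures, and sample size, event targets, alpha and stated power are unchanged.

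If an analysis has already been run, list by arm any participants withdrawn under 6.4 without withdrawing consent and, where consent allows, update their survival status. That would replace the assumed rates above with a count.

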6.5 Concomitant Therapy

All concomitant medications received within 28 days prior to randomization and up to 30 days after the last dose of study intervention should be recorded. Concomitant medications administered >30 days after the last dose of study intervention should be recorded for SAEs as defined in Section 8.4.

All treatments that the investigator considers necessary for a participant's welfare may be administered at the discretion of the investigator in keeping with the community standards of medical care. All concomitant medication will be recorded on the eCRF including all prescription, OTC products, herbal supplements, blood transfusions, supplemental oxygen, and IV medications and fluids. If changes occur during the study period, documentation of drug dosage, frequency, route, and date should also be included on the eCRF.

In vitro and physiologically based PK modeling results indicated that belzutifan is a weak inducer of CYP3A4. Belzutifan may, therefore, decrease the exposure of concomitant medications that are mainly metabolized by CYP3A4, including hormonal contraceptives; however, the clinical relevance of these effects is not clear. Inhibitors of UGT2B17 or CYP2C19 may increase plasma exposure of belzutifan, which may increase the incidence and/or severity of adverse reactions.

Everolimus is a substrate of CYP3A4 and of the multidrug efflux pump P-gp. Refer to the most current everolimus prescribing information about potential drug interactions and appropriate dosage adjustments.

6.5.1 Prohibited Concomitant Medications

Medications or vaccinations specifically prohibited in the exclusion criteria (Section 5.2) are not allowed during screening and during the study intervention phase of the ongoing study, unless noted below. If there is a clinical indication for any medication or vaccination specifically prohibited, discontinuation from study intervention may be required. The investigator should discuss any questions regarding this with the Sponsor Clinical Director. The final decision on any supportive therapy or vaccination rests with the investigator and/or the participant's primary physician. However, the decision to continue the participant on study intervention requires the mutual agreement of the investigator, the Sponsor, and the participant.

Listed below are specific concomitant therapies or vaccinations that are prohibited during the study (exceptions noted):

- 1. Antineoplastic systemic chemotherapy or biological therapy not specified in this protocol.
- 2. Investigational agents other than belzutifan.
- 3. Radiation therapy for disease control.
 - Note: Palliative radiation therapy to symptomatic lesions or to the brain is allowed following Sponsor consultation.

- 4. Live vaccines while participating in the study. Refer to Appendix 7 for country-specific requirements.
 - Examples of live vaccines include, but are not limited to, the following: measles, mumps, rubella, chickenpox, yellow fever, intranasal seasonal influenza, rabies, BCG, and typhoid (oral).

Note: Seasonal influenza vaccines for injection are generally killed virus vaccines and are allowed

- 5. Systemic glucocorticoids for any purpose other than to modulate symptoms from an AE. Corticosteroid replacement therapy for participants with adrenal or pituitary insufficiency is permitted. Note: Inhaled, intranasal, ophthalmologic, intra-articular or intrathecal steroid injections are permitted.
- 6. Use of strong inhibitors of CYP3A4 is not allowed on treatment. If a moderate CYP3A4 inhibitor or a moderate/strong CYP3A4 inducer is required during the study intervention treatment period for participants randomized to belzutifan consult with the Sponsor Clinical Director; for participants randomized to everolimus, refer to the everolimus package insert for guidance.
 - Note: a current list of strong/moderate inducers/inhibitors of CYP3A4 can be found at the following website: https://www.fda.gov/Drugs/DevelopmentApprovalProcess/DevelopmentResources/D rugInteractionsLabeling/ucm093664.htm
- 7. P-gp inhibitors are not prohibited during the study intervention treatment period for participants randomized to belzutifan. If a P-gp inhibitor is required during the study intervention treatment period for participants randomized to everolimus, refer to the everolimus package insert for guidance.
 - Note: a current list of P-gp inhibitors can be found at the following website: https://www.fda.gov/drugs/drug-interactions-labeling/drug-development-and-drug-interactions-table-substrates-inhibitors-and-inducers
- 8. ACE inhibitors are prohibited for those participants receiving everolimus, however, are not prohibited for participants receiving belzutifan.

Participants who, in the assessment by the investigator, require the use of any of the aforementioned treatments for clinical management should be removed from treatment, but continue in study for assessment of disease status and survival.

There are no prohibited therapies during the Survival Follow-up Phase.

